## 5. TREATMENT OF SUBJECTS

### 5.1 Investigational product/treatment

In patients allocated to the intervention group, the carotid artery stenosis will be stented during the EVT. The CAS may be done just before the intracranial thrombus removal or directly after (at the discretion of the interventionist). In case of unsuccessful intracranial reperfusion (TICI score < 2b), it is still recommended to perform CAS. In addition, if the first DSA run demonstrates intracranial recanalization but confirms a high-grade carotid artery stenosis, it is still recommended to perform CAS. Crossover to deferred treatment is strongly discouraged and will be considered a protocol violation unless a valid reason has been reported by the local PIs.

The patients allocated to the control group are being treated with EVT, without stenting of the carotid artery stenosis. Percutaneous transluminal angioplasty (PTA) of the carotid artery stenosis is allowed to gain access in order to remove the intracranial occlusion. Crossover to stenting during EVT is strongly discouraged. Crossovers without a valid reason according to the executive committee will be considered a protocol violation. If the patient recovers to a non-disabling stroke after EVT, CEA or CAS is offered according to the guidelines (usually CEA or CAS within 2 weeks after stroke onset). In case of a persistent disabling stroke, patients receive best medical treatment, without intervention of carotid artery stenosis.

### 5.2 Use of co-intervention (if applicable)

It is highly recommended to give patients allocated to the stenting group a loading dose of 500 mg intravenous aspirin (Aspegic®), just prior to or shortly after stenting (within 1 hour after groin closure), followed by an oral dose of 1x100 mg aspirin and 1x75 mg clopidogrel after 24 hours after the loading dose, and after ruling out intracranial hemorrhage on follow-up brain CT at 24 hours after EVT. Dual antiplatelet treatment is recommended for at least 3 months. If the patient is known to be a poor or intermediate CYP2C19 metabolizer, an oral dose of ticagrelor 2x 90 mg or prasugrel 1x10 mg is allowed. Patients using factor Xa inhibitors, thrombin inhibitors (direct oral anticoagulants (DOACs)) or vitamin K antagonists will not be treated with clopidogrel, but only in combination with aspirin, because the increased risk of hemorrhagic complication with "triple therapy". The use of periprocedural heparin is not recommended as the both intravenous aspirin and heparin increase the risk of intracranial hemorrhage. Prior administration of intravenous thrombolysis should not be of influence for the prescribed antiplatelet regimen. The use of distal protection devices during CAS is discouraged, however, proximal flow arrest with balloon guiding catheter is allowed during CAS. In case of bradycardia that occurs during PTA and/or CAS, it is allowed to administer intravenous atropine. Blood pressure lowering therapy is advised when the systolic blood pressure is above 180 mm Hg, in order to prevent cerebral hyperperfusion. Patients allocated to the control group (no CAS during EVT) are being treated with antiplatelet or antithrombotic therapy according to national or European guidelines.

### **5.3 Escape medication (if applicable)**

In case of periprocedural stent occlusion, the use of tirofiban IV (bolus of 25 microgram/kg followed by 0.15 microgram/kg/min) or eptifibatide IV (bolus of 180 microgram/kg followed by 2.0 microgram/kg/min) is allowed.

## 6. INVESTIGATIONAL PRODUCT

### 6.1 Name and description of investigational product(s)

The invention in this trial is carotid artery stenting during EVT. The comparator is no stenting of carotid artery stenosis during EVT but a deferred treatment of the carotid artery stenose (BMT or CEA/CAS). The approved carotid artery stents are listed below:

Device name	Manufacturer	Description
Roadsaver	Terumo	Carotid artery stent
Casper	Microvention	Carotid artery stent
CGuard	Inspire MD	Carotid artery stent
Wallstent	Boston Scientific	Carotid artery stent
Xact	Abbott	Carotid artery stent
Acculink	Abbott	Carotid artery stent
NexStent	EndoTex	Carotid artery stent
Protégé RX	Medtronic	Carotid artery stent
Precise Pro Rx	Cordis	Carotid artery stent

### 6.2 Summary of findings from non-clinical studies

Not applicable: carotid artery stents are currently being used as a regular treatment of carotid artery stenosis.

### 6.3 Summary of findings from clinical studies

CAS has been shown effective to prevent recurrent ischemic stroke in patients with TIA or non-disabling stroke, although trials that compared CEA with CAS showed a slight superiority of CEA. No randomized controlled trials on CAS have been performed in EVT treated patients. Several retrospective studies have assessed the safety and outcomes of carotid artery stenting during EVT. A summary of these studies, revealed no increased risk of hemorrhagic complications and no worse outcome but even a tendency towards better functional outcome in patients who were stented during EVT. However, several of these studies were prone to selection and publication bias as the number and characteristics of patients having a tandem lesion, not treated with carotid stenting were usually not reported.

### 6.4 Summary of known and potential risks and benefits

The potential risks of stenting the ICA during EVT is an increased risk of:

- Periprocedural emboli in new vascular territories
- Intracerebral hemorrhage due to administration of antiplatelet therapy during EVT necessary to prevent stent thrombosis
- Cerebral hyperperfusion syndrome
- Temporary bradycardia and/or hypotension (due to activation of the carotid baroreceptors)

The potential benefits of stenting the ICA during EVT are:

- Immediate risk reduction of recurrent ischemic stroke
- Improvement of cerebral perfusion
- Avoidance of a second surgical treatment (usually CEA) when the patient recovers after stroke (reduction of health care costs, higher patient satisfaction)

### **6.5 Description and justification of route of administration and dosage**

In the immediate CAS group, 500 mg of aspirin (Aspegic®) will be given intravenously because this will ensure an immediate effect on platelet aggregation (much faster than oral administration). 500 mg is commonly used dose for carotid artery stenting. Clopidogrel will be administered orally in a dose of 75 mg and not with a loading dose, because a loading dose for aspirin was already administered. If the patient is known to be a poor or intermediate CYP2C19 metabolizer, an oral dose of ticagrelor 2x 90 mg or prasugrel 1x10 mg are allowed to be used. Routine platelet function testing during EVT is not recommended.

When there is a strong indication for anti-thrombotic treatment, for instance in case of concomitant atrial fibrillation, it will be advised to start with a direct oral anticoagulant drug (DOAC) or vitamin K antagonist in combination with aspirin (and instead of clopidogrel). The combination of aspirin, clopidogrel and DOACs/vitamin K antagonists, is strongly discouraged, due to the increased hemorrhage risks.

### **6.6 Dosages, dosage modifications and method of administration**

In the intervention group, the following medication protocol is recommended:

- Aspirin dose: Aspegic® 500 mg intravenously during or shortly after carotid artery stenting (within 1 hour after groin closure), followed the next day by oral dose of 100 mg daily
- Clopidogrel dose 24 hours after EVT, after ruling out intracranial hemorrhage on follow-up brain CT at 24 hours after EVT: oral dose of 75 mg daily

Dual antiplatelet therapy is recommended for a period of 3 months (standard of care after CAS), thereafter the treatment will be as recommended by the guidelines (usually monotherapy clopidogrel 75 mg daily, alternative aspirin 100 mg daily in combination with dipyridamole 2 time 200 mg).

### **6.7 Preparation and labelling of Investigational Medicinal Product**

N/A

### **6.8 Drug accountability**

The used medication is a standard treatment for this specific population. Additional drug accountability is not necessary

## 7. NON-INVESTIGATIONAL PRODUCT

### 7.1 Name and description of non-investigational product(s)

EVT will be performed with either stent retriever or thrombus aspiration catheters at the discretion of the interventionist. Devices approved for this study are listed in the table below. If necessary the use PTA of the carotid artery stenosis is allowed in the control group.

Device name	Manufacturer	Description
Embotrap	Cerenovus	Stent retriever
Eric	Microvention	Stent retriever
Solitaire	Medtronic	Stent retriever
Catch	Balt	Stent retriever
Preset	Phenox	Stent retriever
Trevo	Stryker	Stent retriever
Tigertriever	RapidMedical	Stent retriever
Nimbus	Cerenovus	Stent retriever
NeVa	Vesalio	Stent retriever
ACE64/68/Red	Penumbra	Aspiration catheter
4Max	Penumbra	Aspiration catheter
3Max	Penumbra	Aspiration catheter
Sofia 5F or Sofia Plus	Microvention	Aspiration catheter
Embovac	Cerenovus	Aspiration catheter
Catalyst	Stryker	Aspiration catheter
AXS Vecta	Stryker	Aspiration catheter
React	Medtronic	Aspiration catheter
Merci	Stryker	Balloon guiding catheter
Flowgate2	Stryker	Balloon guiding catheter
Cello	Medtronic	Balloon guiding catheter

### 7.2 Summary of findings from non-clinical studies

Not relevant, as all devices are CE marked and approved for clinical use as intended.

### 7.3 Summary of findings from clinical studies

Several randomized controlled trials have demonstrated the efficacy of EVT by the use of stent retrievers, aspiration catheters or a combination of both. The number needed to treat to prevent one patient from becoming disabled varies between 3-7. EVT is currently standard of care for stroke patients with large vessel occlusion. The treatment of carotid

artery tandem lesions during EVT is a matter of debate and there is a lot of practice variation among interventionist. In retrospective cohort studies, there were no major differences observed in clinical outcome or the safety endpoints between the immediate CAS group and deferred treatment group.

#### **7.4 Summary of known and potential risks and benefits**

The risks and benefits of immediate stenting the carotid artery have been described in 6.4. Without immediate stenting there is an increased risk of recurrent ischemic stroke or early carotid artery (re-)occlusion. The other major disadvantage is that in case of recovery to a non-disabling stroke, the patient will have to undergo surgery later, extending hospital stay and exposing the patient to a second procedure with associated risks.

#### **7.5 Description and justification of route of administration and dosage**

See also 6.5

#### **7.6 Dosages, dosage modifications and method of administration**

See also 6.6

#### **7.7 Preparation and labelling of Non Investigational Medicinal Product**

Not applicable, see 6.7

#### **7.8 Drug accountability**

Not applicable, see 6.8

## 8. METHODS

### 8.1 Study parameters/endpoints

#### 8.1.1 Main study parameter/endpoint

The primary outcome is the modified Rankin Scale Score at 90 days after stroke onset. The mRS is a disability scale ranging from 0 (no symptoms at all) to 6 (death). The mRS score will be assessed by a stroke research personnel by telephone interview, blinded for the treatment allocation.

#### 8.1.2 Secondary study parameters/endpoints (if applicable)

Secondary endpoints are:

- mRS score of 0-1 at 90 days
- mRS score of 0-2 at 90 days
- mRS score of 0-3 at 90 days
- NIHSS score at 24 hours and day 5-7, or at discharge
- adequate recanalization after EVT (TICI 2b or higher)
- final infarct volume on brain CT at 24 hours
- arterial occlusive lesion (AOL) score on CTA at 24 hours
- any stroke within 90 days
- recurrent ipsilateral TIA/ischemic stroke within 90 days
- Carotid artery re-occlusion at 24 hours and 90 days.
- Mortality at 90 days
- Quality of life (EQ5D-5L) questionnaire at 90 days

For the purpose of health economic evaluation, additional questionnaires will be sent to the study participants at 90 days for measuring loss of productivity (IMTA productivity cost questionnaire (iPCQ)) and medical consumption (IMTA medical consumption questionnaire (iMCQ)).

#### 8.1.3 Safety outcomes

- Incidence of symptomatic intracerebral hemorrhage (Heidelberg criteria)
- Asymptomatic intracerebral hemorrhage on brain CT at day 1
- Subarachnoid hemorrhage on brain CT at day 1
- Any extracranial hemorrhage within 90 days
- Embolization in new vascular territories during EVT
- Incidence of complications at the vascular access site (aneurysm, bleeding, vascular occlusion) within 72 hours after the intervention
- Incidence of bradycardia and/or hypotension during CAS
- Serious adverse events (renal function disorder, myocardial infarction, gastrointestinal bleeding)

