## **2. OBJECTIVES**

The primary objective of this trial is to assess the efficacy of immediate CAS among patients with acute ischemic stroke treated with EVT and a severe ipsilateral proximal carotid artery stenosis (>50%) or occlusion and compare this with the strategy of deferred treatment (including best medical treatment without CEA/CAS) of the proximal carotid artery stenosis according to the guidelines.

The secondary objective is to compare the safety of the two strategies (immediate CAS versus deferred treatment) regarding the incidence of symptomatic intracerebral hemorrhage, recurrent stroke and early proximal carotid artery re-occlusion.

The tertiary objective is to compare the quality of life and cost-effectiveness of both strategies.

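### Two procedural safety outcomes in 8.1.3 (bradycardia/hypotension and access-site complications) are counted unevenly between the strategies, which tilts those two rows against immediate CAS

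*Protocol*

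**What the plan says.** Protocol section 8.1.3 lists eight safety outcomes. Two matter here:

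- "Incidence of bradycardia and/or hypotension during CAS"
- "Incidence of complications at the vascular access site (aneurysm, bleeding, vascular occlusion) within 72 hours after the intervention"

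The control strategy can involve two further carotid procedures. Section 5.1 allows PTA during EVT to gain access. For patients who recover to a non-disabling stroke it also offers later revascularization ("usually CEA or CAS within 2 weeks after stroke onset"). Section 5.2 links bradycardia to PTA as well as stenting: "In case of bradycardia that occurs during PTA and/or CAS, it is allowed to administer intravenous atropine". Section 7.4 describes the deferred route as "extending hospital stay and exposing the patient to a second procedure with associated risks".

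Section 10.1 has the safety endpoints analysed in the full analysis set and the per-protocol set, both as randomised, and in the safety set, which goes by treatment received.

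**The concern.** The trial compares strategies, and one strategy includes a second carotid procedure in some patients. An outcome tied to a procedure that mainly one arm undergoes, or to a window that closes before the other arm's second procedure, records harm in one arm and cannot record the matching harm in the other. The difference in such a row then partly reflects the definition. The safety table would show more haemodynamic and access-site complications with immediate CAS than a like-for-like count would, and avoiding a second procedure is one of the protocol's stated reasons for immediate CAS.

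**Working it through.** The protocol gives no figure for these outcomes, so there is none to reproduce. The check is to read each outcome for the procedure and window it depends on.

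**Bradycardia/hypotension (8.1.3), by procedure**

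- CAS during EVT, intervention arm: counted, and nearly every patient is exposed by design.
- PTA without a stent during EVT, control arm: not counted, although 5.2 anticipates bradycardia there.
- Deferred CEA, control arm: not counted.
- Deferred CAS, control arm: counted as worded, because the line does not say index CAS.

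A control with neither deferred nor crossover CAS is therefore a structural zero. The safety set adds an ambiguity: 10.1 does not say how a control with a deferred stent is classed. If that patient were moved to the stented group, the remaining controls could have no events in this row at all.

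**Access-site complications (8.1.3)**

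- Index EVT access: counted in both arms in the same way.
- Deferred CEA or CAS: depends on what the intervention means, which the protocol does not state. Read as the index session, the 72 hours are over before a procedure done up to 2 weeks later would normally take place.
- A CEA wound is in any case not clearly a vascular access site.

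**Remaining safety and related outcomes**

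- "Embolization in new vascular territories during EVT": every patient in both arms has EVT, so the window is the same in both. This is an index-procedure outcome and is not tilted.
- Day-1 CT findings: the same assessment in both arms.
- Symptomatic intracerebral hemorrhage: no index-session limit.
- Extracranial hemorrhage: to 90 days.
- Serious adverse events, including myocardial infarction: not tied to a procedure.
- Any stroke, recurrent ipsilateral TIA/ischemic stroke and mortality to 90 days, and re-occlusion at 24 hours and 90 days (8.1.2): both arms.

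**Scale, for illustration only.** The documents give neither the share of controls who have a second procedure nor its complication risk, so both are assumed.

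- Formula: uncounted events = 300 × share × risk, with 300 controls from section 4.5.
- Share: 30% as an assumed low value. As upper proxies, the deferred registry group in 4.5 has mRS 0–2 = 6.9 + 20.2 + 17.9 = 45.0%, and mRS 0–3 = 45.0 + 16.4 = 61.4%.
- Second procedures: 300 × 0.30 = 90; 300 × 0.45 = 135; 300 × 0.614 ≈ 184.
- Risk: 2% to 10%, assumed.
- Low end: 90 × 0.02 = 1.8. Middle: 135 × 0.05 ≈ 6.8. High end: 184.2 × 0.10 ≈ 18.4.

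This is about 2 to 18 events, or 0.6% to 6.1% of the control arm. It is not an estimate. Ninety-day mRS is a poor stand-in for a decision usually acted on within 2 weeks, and the two proxies assume every such patient has the procedure. Bleeding at the site is already caught by the 90-day extracranial hemorrhage outcome, and haemodynamic events during a deferred CAS are already counted. On the other side, the calculation leaves out haemodynamic events during control-arm PTA, for which the documents give no frequency.

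**The case against.** The strongest reply is that the safety objective does not rest on these rows. Section 2 says "The secondary objective is to compare the safety of the two strategies (immediate CAS versus deferred treatment" and then names symptomatic intracerebral hemorrhage, recurrent stroke and early re-occlusion. None of these is tied to the index session. This stands, and it limits the point to two secondary rows.

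A reader might infer that harm from the second procedure goes largely uncounted, or that the trial cannot measure the benefit of avoiding it. The documents do not support that. Stroke, death, extracranial hemorrhage and serious adverse events are counted in both arms, section 9.2.1 records all reported or observed adverse events, and the 90-day mRS reflects any lasting effect. Nor do all procedural outcomes look at the index session only: a deferred CAS falls within the haemodynamic line as worded, and embolization has the same window in both arms.

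Two further replies carry less weight. The first is that bradycardia and hypotension are a temporary stenting risk (section 6.4) and the row is descriptive. Section 10.1 makes no such exception and takes safety endpoints through all three analysis sets. The second is that the anchors may be given in the statistical analysis plan, which is not shown. That could settle the 72-hour wording, but these definitions also drive what sites are asked to record. Spontaneous or observed adverse-event reports do not replace an outcome sought equally in both arms. Section 8.1.4 records details of deferred treatment, but complications are not among its examples.

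**Conclusion.** The point holds for two outcomes. Bradycardia/hypotension leaves out control-arm PTA and deferred CEA, and it conflicts with the protocol's own description of when bradycardia occurs. The access-site window has no defined anchor and, if read as the index session, misses the deferred procedure. Both rows are tilted against immediate CAS when the arms are compared. The access-site part rests on that reading; the haemodynamic part follows from the wording alone.

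The size of the tilt cannot be derived from the documents, and the range above rests on assumed shares and risks. The main safety outcomes and the non-inferiority decision on the mRS are unaffected. This is an inexpensive improvement to outcome definitions. It does not show that the safety comparison as a whole is biased.

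**What to change.** In 8.1.3:

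1. Define bradycardia/hypotension as occurring during EVT or any carotid revascularization procedure (PTA, CAS or CEA) up to day 90.
2. Define access-site complications as occurring within 72 hours after EVT, and within 72 hours after any deferred CAS or CEA up to day 90, covering the access site or surgical wound.
3. Compare both by randomised strategy, and report index-session events separately as description.
4. Label embolization as an outcome of the index EVT.

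The cost is protocol wording and a repeat of the existing complication items for the deferred procedure, so some extra data entry for controls who have one. No treatment, sample size or primary analysis changes.

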#### **8.1.4 Other study parameters**

Event characteristics such as prehospital and intra-hospital time intervals will be documented (such as but not limited to: stroke onset, arrival time primary and comprehensive stroke centers, prior IVT, arrival time angiosuite, time of groin puncture, time of recanalization, time of stent placement and end of procedure,). Baseline demographics, medical history, comorbidities and vascular risk factors will be recorded (such as but not limited to: age, sex, prestroke mRS, previous stroke, previous myocardial infarction, hypertension, hyperlipidemia, diabetes mellitus, atrial fibrillation, peripheral vascular disease, smoking status). Medication at baseline and during follow-up will be assessed (such as but not limited to: antiplatelet therapy, anticoagulant therapy, antihypertensive treatment, lipid lowering drugs). Other variables that will be recorded are: NIHSS score, GCS score, vital parameters, laboratory results (such as but not limited to: renal and liver function, glucose, thrombocytes, CRP), and multiple imaging characteristics (such as but not limited to ASPECTS score on non-contrast CT, infarct core volume, penumbra volume, location of intracranial occlusion on CTA and DSA). Various details regarding the endovascular treatment, study treatment and deferred treatment will be recorded (such as but not limited to: periprocedural general/local anesthesia or conscious sedation, stent type, administration of medication during and after EVT).

#### **8.2 Randomization, blinding and treatment allocation**

The randomization will be performed by a computer and web-based procedure, using permuted blocks. Back-up by telephone will be provided. Randomization is allowed when the CTA at baseline demonstrates an ipsilateral high-grade stenosis (>50%) or occlusion of the proximal ICA of presumed atherosclerotic origin. Although DSA is more reliable to distinguish carotid pseudo-occlusions from cervical atherosclerotic lesions in the ICA, randomization during the EVT can be very challenging and might lead to lower inclusion rates. And CTA has been shown to have acceptable diagnostic accuracy for true cervical ICA lesions. Only in case of significant doubt by the interventionist if there is a true cervical atherosclerotic lesion in the carotid artery, randomization is also allowed after the first angiographic run of the carotid artery that confirms the cervical atherosclerotic lesion. Randomization will be stratified for center. Both the patient and treating physicians are aware of the treatment assignment. The 90 days follow up will be performed by certified research personnel blinded for the treatment allocation. The assessment of secondary endpoints will not be blinded as for several secondary endpoints it will be obvious whether the patient was treated with CAS or not. Information on treatment allocation will be kept separate from the main study database. An independent trial statistician will combine the data on treatment allocation with the clinical data in order to report to the data safety monitoring board (DSMB). The trial steering committee will be kept unaware of the exact results of the interim analyses on efficacy and safety. Only the recommendation to continue, modify or stop the trial will be communicated.

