**Main study parameters/endpoints:** the primary endpoint is the modified Rankin Scale (mRS) score at 3 months after stroke onset. Ordinal logistic regression analyses will be done with adjustment for prognostic variables: age, sex, baseline NIHSS, prestroke mRS score, collateral score on baseline CTA and onset to reperfusion time.

**Nature and extent of the burden and risks associated with participation, benefit and group relatedness:** All patients are being treated with EVT according to the local guidelines. The patients allocated to the intervention group will undergo CAS during EVT, which carries a risk of cerebral hyperperfusion syndrome and subsequent intracerebral hemorrhage. The potential benefits of immediate CAS during thrombectomy include: an improvement of cerebral blood flow during and after EVT. A second benefit is a lower risk of recurrent stroke in the first 14 days compared to the deferred treatment strategy. A third benefit of immediate CAS is that the patient does not need a second invasive treatment (carotid revascularization surgery (CEA or CAS) during the rehabilitation period which again carries some risk of complications. At last, the immediate CAS approach is likely to reduce health care costs.

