For the sample size calculation, we used data from the Dutch MR CLEAN registry, a nationwide cohort of EVT treated patients between 2014-2018. Based on the mRS distributions in the immediate CAS group (mRS 0: 17.9%, mRS 1: 22.3%, mRS 2: 16.7%, mRS 3: 14.4%, mRS 4: 12.3%, mRS 5: 5.0%, mRS 6: 11.4%) and in the deferred treatment group (mRS 0: 6.9%, mRS 1: 20.2%, mRS 2: 17.9%, mRS 3: 16.4%, mRS 4: 17.2%, mRS 5: 8.0%, mRS 6: 13.4%), we calculated the assumed effect size to be a common odds ratio (cOR) of 1.15 for a shift in favorable direction on the full mRS. The non-inferiority margin was set to a cOR of 0.8, corresponding to an absolute difference of approximately 5% in favorable outcome (mRS 0-2). This is a generally accepted margin in the stroke research community and has been recently used in comparable EVT trials. We used Monte Carlo simulations with 5000 runs to calculate the required sample size based on the assumptions above showing that a sample size of 610 patients, would provide 80% power (at a two-sided alpha level of 0.05) to determine that the lower bound of the cOR 95% confidence interval (CI) does not cross the non-inferiority margin of 0.8. Covariate adjustment for major prognostic variables that included age, pre-stroke mRS score, stroke severity, collateral score and time from symptom onset to randomization results in a reduction of at least 15% in the required sample size (n=520). Assuming a crossover rate of 3% in each arm (6% for both groups), necessitates an increase in sample size by factor  $1/(1 - \% \text{ crossover})^2 = 1/(1 - 0.06)^2 = 1.13$ . So taking crossovers into account, the sample size increases to 588 (520\*1.13). Based on the experience of the MR CLEAN NO-IV trial and MR CLEAN-MED trial, the number of patients lost to follow up is expected to be low

(0 in both recently completed trials). Assuming a combined percentage of 2% due to loss to follow up and to erroneous inclusions (for example inclusion of patients who appear to have carotid dissection or carotid pseudo-occlusion) the sample size will need to be increased to a total sample size of 600 patients (n= 300 per group).

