### **10.2 Primary study parameter(s)**

The primary effect parameter will be expressed by a common odds ratio, estimated with ordinal logistic regression, evaluating a shift on the mRS score at 90 days after randomization. The common odds ratio will be estimated with proportional odds regression adjusted for age, baseline NIHSS score, pre-stroke mRS score, collateral score on baseline CTA and onset to reperfusion time. Both unadjusted and adjusted estimates will be reported with 95% confidence intervals.

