### **10.3 Secondary study parameter(s)**

Secondary effect parameters will be assessed with linear, logistic or ordinal regression, where appropriate, with the same adjustments as reported in 10.1.

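### Randomization is stratified by center, but the listed covariates of the primary and secondary models omit it; adding center is a minor, nearly free improvement

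*Protocol*

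**What the plan says.** Section 8.2 of the protocol describes web-based randomization in permuted blocks: "Randomization will be stratified for center". It names no other stratification factor.

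Covariates are listed in three places, and center is in none of them:

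- Section 10.2, primary model: "adjusted for age, baseline NIHSS score, pre-stroke mRS score, collateral score on baseline CTA and onset to reperfusion time".
- Summary: "adjustment for prognostic variables: age, sex, baseline NIHSS, prestroke mRS score, collateral score on baseline CTA and onset to reperfusion time". This list adds sex.
- Section 4.5, in the sample size argument: "age, pre-stroke mRS score, stroke severity, collateral score and time from symptom onset to randomization".

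Section 10.3 analyses the secondary endpoints "with the same adjustments as reported in 10.1". Section 10.1 defines the analysis sets and contains no adjustments, so 10.2 is presumably meant. On either reading center does not enter.

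**The concern.** When treatment is allocated in permuted blocks within centers, the arms are balanced on whatever differs between centers. An analysis that leaves center out does not use that balance: its standard error is computed as if center differences could fall unevenly between the arms. The odds ratio is also not collapsible, so omitting a prognostic factor pulls the estimate toward 1.

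Both effects bear on the primary decision, which reads the lower limit of a 95% confidence interval against a fixed margin (section 4.5: "The non-inferiority margin was set to a cOR of 0.8"). Section 10 requires that result in both the intention-to-treat and the per-protocol analysis. Some center effect on the mRS is plausible: the trial covers two countries, and section 1 describes wide variation in practice.

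Section 10.2 names its covariates and does not leave them to be chosen later. This is therefore a stated analysis, not a detail left open.

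**Working it through.** **The plan's own figure.** Section 4.5 assumes a "common odds ratio (cOR) of 1.15 for a shift in favorable direction on the full mRS" and gives 610 patients for 80% power at two-sided 0.05. The Whitehead formula for proportional odds is

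N = 12(z_α + z_β)² / {[ln(1.15/0.8)]² (1 − Σp̄³)}.

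With z_α = 1.960, z_β = 0.842, ln(1.15/0.8) = 0.363 and 1 − Σp̄³ ≈ 0.973 from the deferred-arm mRS distribution, N is about 735, and power at 610 is about 72%. So 610 is not reproduced at two-sided 0.05. The later steps are: 610 × 0.85 = 518.5 (about 520), 520 × 1.13 = 588, and 588/0.98 = 600. Center enters none of these steps. The mismatch at 610 is thus a separate matter, and adding center does not change the stated N.

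**Simulation inputs.** From the protocol: N = 600, 1:1 allocation, permuted blocks within center, the deferred-arm mRS distribution, cOR 1.15 or 0.8, and non-inferiority if the lower 95% limit exceeds 0.8. Assumed, because the protocol does not give them: 20 centers of unequal size, blocks of 4, and a between-center SD of 0, 0.3, 0.5 or 0.8 on the log-odds scale. There were about 2,500 runs per scenario. Each trial was analysed with treatment alone and with treatment plus fixed center effects, merging centers with fewer than 8 patients. The other prognostic covariates were left out, so the power levels serve only to compare the two analyses.

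**True cOR 1.15**

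| Center SD | Median cOR without / with center | True SD of estimate, without | Mean model SE, without | SE ÷ true SD | Power without | Power with |
|---|---|---|---|---|---|---|
| 0 | 1.151 / 1.155 | 0.1435 | 0.1436 | 1.001 | 71.72% | 71.52% |
| 0.3 | 1.145 / 1.152 | 0.1414 | 0.1436 | 1.016 | 71.51% | 71.15% |
| 0.5 | 1.140 / 1.152 | 0.1384 | 0.1436 | 1.038 | 70.44% | 71.04% |
| 0.8 | 1.137 / 1.156 | 0.1315 | 0.1435 | 1.091 | 69.91% | 71.39% |

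**True cOR 0.8, at the margin**

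| Center SD | Median cOR without center | Type I error without | Type I error with |
|---|---|---|---|
| 0 | 0.799 | 2.80% | 2.96% |
| 0.3 | 0.799 | 2.68% | 2.76% |
| 0.5 | 0.804 | 2.60% | 2.92% |
| 0.8 | 0.816 | 2.52% | 2.68% |

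The nominal level is 2.5%. Its Monte Carlo standard error is √(0.025 × 0.975/2500) ≈ 0.3 points.

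**Reading the tables.** Without center, the SE overstates the true variability by about 2%, 4% and 9% at SD 0.3, 0.5 and 0.8. The estimate drifts toward 1; at the margin that drift favours non-inferiority, but the conservative SE offsets it and the error rate stays near nominal. The power gain is 0.60 points at SD 0.5 and 1.48 points at SD 0.8, with none at SD 0 or 0.3.

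Fixed center effects have a small cost of their own. Their mean SE is slightly below the true SD, for example 0.1442 against 0.1473 at SD 0.5 (ratio 0.979).

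**The case against.** **Adding center does not narrow the interval.** A reader might infer that the interval is too wide by whatever share of outcome variation center explains, and that modelling center would recover that share. This is linear-model reasoning. In a second set of simulations (about 3,000 runs, same N and number of centers), the model SE without and with fixed center effects was 0.1437 and 0.1444 at SD 0.2, 0.1437 and 0.1445 at SD 0.3, and 0.1436 and 0.1447 at SD 0.5. The interval widens slightly, and any gain comes from the estimate moving away from 1. The latent-variance share τ²/(τ² + π²/3) is 1.2%, 2.7% and 7.1% at τ = 0.2, 0.3 and 0.5, but it measures neither interval width nor power. This objection stands.

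**The decision is not endangered.** Type I error is near 2.5% with or without center, and power hardly moves at SD 0.5 or below. This stands too and limits the point to a minor one.

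**The low experience threshold is not a reason for this fix.** Section 4.2 admits interventionists with as few as five carotid stenting procedures, which might suggest center effects. That experience would act mainly in the stented arm. It would be treatment-by-center heterogeneity, which a random intercept does not capture. The same section also sets thrombectomy volume and trial experience criteria, which limit center differences.

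**The SAP may settle it.** How a stratification factor enters a model is often left to the SAP, which was not available here, and 10.2 does not say its list is exhaustive. This lowers the weight of the point but does not remove it. A SAP that follows 10.2 as written would omit center, and one that adds it would depart from the listed model.

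**Conclusion.** The design and the stated analysis do not match: center is the sole stratification factor and is absent from every covariate list. The consequence is a slightly conservative standard error, mild attenuation of the common odds ratio and a power difference that is negligible at SD 0.5 or below. A reader might infer that the non-inferiority test is invalid, or that omitting center explains a shortfall in power. Neither follows from the documents or the simulations.

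The textual fact is certain. The sizes rest on the assumed 20 centers, block size and between-center SDs, and on fixed center effects; the random intercept was not simulated. This is a minor point, worth taking because it costs almost nothing and settles in advance which odds ratio is compared with 0.8.

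**What to change.** - **Section 10.2:** add center to the proportional-odds model, preferably as a random intercept because some centers may be small. The alternative is fixed effects with a pooling rule for small centers, set in advance.
- **Section 10.3:** carry center into the secondary models and change the reference from 10.1 to 10.2.
- **Summary and SAP:** bring the covariate list into line with 10.2.

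The cost is one phrase in 10.2, a corrected cross-reference and matching text elsewhere. Center is already known from the stratified randomization, so no new data are needed, and the sample size is unaffected. The change should be made before the efficacy interim analysis at 300 patients (section 9.5), so that it precedes any view of outcomes by arm.
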